16.2.1.2.2. SGRQ

St. George's Respiratory Questionnaire (SGRQ) is a questionnaire consisting of 17 questions, split into two parts. Part 1 consists of the first 8 questions and is related to the Symptoms subdomain. The remaining 9 questions are in Part 2, which are related to the Activity and Impacts subdomains. Each possible answer to each question has a weight assigned described in the Appendix 5.

Note that question 6 (How long did the worst respiratory attack last?) has an additional instruction, “Go to Question 7 if you did not have a severe attack”. If question 6 has not been answered, it will be assigned a weight of zero.

Calculating the score

Subdomains:

- Symptoms – items 1 to 8
- Activity – items 11 and 15
- Impacts – items 9, 10, 12, 13, 14, 16 and 17

The score for each component is calculated separately by dividing the summed weights by the maximum possible weight for that component and expressing the result as a percentage. It is not possible to have missing items in the questionnaire, as the data are collected in an electronic tablet which doesn’t allow patients to skip between items.

$$\text{Component score} = 100 * \frac{\text{Sum of weights from all positive items in that component}}{\text{Sum of maximum weights for all items in that component}}$$

The total score is calculated similarly

$$\text{Total score} = 100 * \frac{\text{Sum of weights from all positive items in that questionnaire}}{\text{Sum of maximum weights for all items in that questionnaire}}$$

The higher the score the more severe impact of COPD on patient’s life.

Sum of maximum possible weights for each component and Total:

Symptoms = 662.5

Activity = 1209.1

Impacts = 2117.8

Total = 3989.4

16.2.1.2.3. **BDI/ TDI**

Baseline Dyspnea Index (BDI) and Translational Dyspnea (TDI) are questionnaires that focus on three subdomains: Functional impairment, Magnitude of task and Magnitude of effort. BDI is collected at baseline (Day 1) and TDI is collected post-baseline (Weeks 6, 12 and 24).

Subdomain score is calculated as the sum from the related questions. Total score is calculated as the sum of the subdomain scores.

If at least one of the scores is missing, then total score is set to missing.

16.2.1.3. Rescue Medications

Baseline use of rescue medication is the mean over the last 7 days of run-in phase, using only days where data was recorded:

$$\frac{\text{Sum of number of puffs taken}}{\text{days recorded}}$$

Use of medication per week is calculated as the mean use daily over 7 days, as described in the windowing conventions Section of the SAP, calculated only based on the days data was recorded/verified.

If less than 4 days of data are available for the week, the weekly mean is set to missing. If a patient discontinued then use study discontinuation end date, as the date of their last expected data input.

This will be documented as Albuterol/Salbutamol in the “Rescue Medication” page of the eCRF, as well as in the “Rescue Medication Use” diary entry.

The rescue medication use will be confirmed in the diary using the following rules:

1. If patient has put in rescue medication use then analyze as expected.
2. If patient has not put in rescue medication use, then to confirm that there was no diary compliance issue, or IT issue, question “No Rescue Medication Confirmation” will be checked to make sure it is filled in correctly.
3. If patient has not put in rescue medication use and question “No Rescue Medication Confirmation” was not filled in correctly then this will be treated as diary compliance or IT issue and therefore this day will not be used as the day recorded for the weekly means calculation.

16.2.2. MISSING DATA METHODS FOR SECONDARY EFFICACY VARIABLES

16.2.2.1. MI method – continuous data

The analysis for key secondary endpoints (FEV₁ AUC_{0-4h}, peak FEV₁, morning trough FEV₁, SGRQ total score and weekly mean E-RS total score) and for evening trough FEV₁ and weekly rescue medication will be performed using MI based on the missing data assumption MAR. This process will follow four steps (below the example uses baseline FEV₁, but it is repeated also for baseline of other key secondary endpoints mentioned above, excluding the ones evaluated weekly):

1. Partially impute the data for a monotone missing pattern with 100 as a number of imputations and “20905” as seed number. Employ the Markov Chain Monte Carlo (MCMC) method with treatment, region, background medication strata, smoking strata, baseline FEV₁ and <Visit data>. <Visit data> corresponds to all scheduled visits available for the parameter analyzed. Each visit will correspond to a covariate within the model.

The following SAS codes will be used:

```
proc mi data=<data1> out=<data2> nimpute=100 seed=20905;
  var <treatment> <region> <BackgroundMedStrata> <SmokingStrata>
  <baseline> <visits>;
  mcmc impute=monotone chain=multiple;
run;
```

2. Impute the monotone data using a regression imputation model. Apply by imputation using seed number “20905” with treatment, region, background medication strata, smoking strata, baseline FEV₁ and <Visit data>.

The following SAS codes will be used:

```
proc mi data=<data2> out=<dataout> nimpute=1 seed=20905;
  by imputation ;
  class <treatment> <region> <BackgroundMedStrata>
  <SmokingStrata>;
  var <treatment> <region> <BackgroundMedStrata> <SmokingStrata>
  <baseline> <visits>;
  monotone regression;
run;
```

3. Each multiple imputed dataset in Step 2 will be analyzed separately, as described in Section 16.2.3 of the SAP.
4. The estimates (LS means, SE, CI and p-value) from the model analysis in Step 3 will be combined using Rubin’s combination rules for statistical inference.

Note: For secondary endpoints that are evaluated weekly, the following updates will be implemented for the first 2 steps:

1. MI model will contain weekly means at all weeks available to impute the data to create a monotone missingness pattern, so will be imputed missing values at any week (i.e. Week 1, Week 2, ...).
2. After this, the fully imputed dataset will include weekly means at weeks corresponding to scheduled visits in the MI model, and also only impute missing values at weeks corresponding to scheduled visits.

16.2.2.2. MI method – binary data

For the analysis of proportion of SGRQ, weekly mean total E-RS and Morning trough FEV₁ responders, an analysis will be performed using MI based on the missing data assumption MAR. This process will impute the continuous underlying data, as per 16.2.2.1 (morning trough FEV₁, SGRQ total score and weekly mean total E-RS), and then recalculate the binary outcome of responder or non-responder. The analysis will follow the steps below (Ratitch and O’Kelly, 2014, pp.124 - 127) (below the example uses morning trough FEV₁, but it is repeated also for other endpoints mentioned above):

- 1) Follow steps 1 and 2 from 16.2.2.1 for the continuous morning trough FEV₁ results.
- 2) For the imputed results re-calculate response, where a response is an improvement from baseline in morning trough FEV₁ of 100 mL.
- 3) Analyse each multiply imputed dataset separately, as described in Section 16.2.3 of the SAP, producing LS Means, odd ratios and corresponding 95% confidence interval and p-value.
- 4) For the odds ratios:
 - a) Before applying Rubin’s rule, apply a normalising transformation to the odds ratios as well as their standard errors. The distribution of the log of odds ratios approximates to a normal distribution. Therefore, calculate the transformed values, where OR is odds ratio, Lower/Upper CL are the confidence interval estimates of the ORs:

$$OR_{norm} = \log(OR)$$

$$SE_{norm} = \frac{(\log(Upper\ CL) - \log(Lower\ CL))}{(2 \times 1.96)}$$

- b) Apply Rubin’s rule with PROC MIANALYZE to the transformed odds ratios with corresponding transformed standard errors.
- c) Back-transform the combined results as follows:

$$OR_{bt} = \exp^{OR_{norm}}$$

$$Lower\ CL_{bt} = OR_{bt} \times e^{(-1.96 \times SE_{norm})}$$

$$Upper\ CL_{bt} = OR_{bt} \times e^{(1.96 \times SE_{norm})}$$

- 5) For the odds of response per treatment arm.
 - a) Take the LS means to be estimates of the log-odds of response per treatment arm and assume that they asymptotically tend to follow a normal distribution.
 - b) Apply Rubin’s rule with PROC MIANALYZE to the LS means.
 - c) Transform the combined results by exponentiating to get the odds of response per treatment arm.

[REDACTED]

[REDACTED]

[REDACTED]

[REDACTED]

[REDACTED]

16.2.2.3. MI method – range data

The sensitivity analysis for key secondary endpoints (SGRQ total score and weekly mean E-RS total score) and the main analysis of TDI will be performed using MI based on the missing data assumption MAR as described in the Section 16.2.2.1 of the SAP. Additionally, in the first 2 steps the MIN= and MAX= options will be used to restrict the possible values that can be drawn referred to each endpoint (Laura Rodwell, 2014).

16.2.2.4. Other methods

As a sensitivity analysis, other missing data method for key secondary endpoints will follow the average imputation and tipping point approach taken for primary endpoint outlined in Section 16.1.2 of the SAP.

16.2.3. ANALYSIS OF SECONDARY EFFICACY VARIABLES

16.2.3.1. Change from baseline variables, incl. TDI

All variables used in change from baseline analysis (incl. average FEV₁ AUC_{0-4h}, peak FEV₁, morning trough FEV₁, evening trough FEV₁, mean weekly E-RSTM:COPD, SGRQ, mean weekly rescue medication and TDI) will be analyzed using ANCOVA approach, as described in Section 16.1.3 of the SAP. BDI will be used as a baseline for TDI. Missing data will be imputed using imputation described in Section 16.2.2 of the SAP. Continuous method will be used for lung function endpoints and the main analysis. Range method will be used for corresponding sensitivity analyses of SGRQ total score and weekly mean E-RS total score and the main analysis of TDI.

Model assumptions will be tested and solved, if failed, as per Section 16.1.3 of the SAP.

A plot of the mean change from baseline FEV₁ to each post-dose FEV₁ result over time will be created by subgroups of actual background medication strata and actual smoking strata, visit and treatment group.

A plot of the least squares means change from baseline to event over time will be presented (based on the ANCOVA analysis). Events will include weekly mean total E-RS score, SGRQ and weekly mean rescue medication use.

Only FEV₁ measurements with BTR grades “Acceptable” and “Borderline Acceptable” are used in the analysis.

[REDACTED]

16.2.3.2. Proportion of SGRQ total responders

Proportion of responders, with an improvement from baseline in SGRQ total score of 4 or more will be analyzed using a logistic regression model with fixed effects for treatment, region, actual background medication strata and actual smoking strata at baseline and baseline SGRQ total score as covariate. Missing data will be imputed as described in Section 16.2.2.3 (range method).

16.2.4. SENSITIVITY ANALYSIS OF SECONDARY EFFICACY VARIABLES

For the key secondary endpoints the following sensitivity analysis will be performed at Week 12.

- Subgroup analysis as specified in Section 7.5 of the SAP.
- ANCOVA analysis with average imputation, as described in Section 16.1.2 of the SAP.
- ANCOVA analysis with MI, only considering baseline and Week 12 (for lung function parameters) in the imputation model, as described in Section 16.1.2 and 16.1.3 of the SAP.
- ANCOVA analysis with MI using the range data method as described in Section 16.2.2.3 for SGRQ total score and weekly mean total E-RS.
- Tipping point approach, as described in Section 16.1.2 of the SAP.
- Analysis with MI method, as described in Sections 16.2.2 and 16.2.3 of the SAP, based on PP population.
- For FEV₁ key secondary endpoints (FEV₁ AUC_{0-4h}, peak FEV₁, morning trough FEV₁) additional sensitivity analysis will be performed:
 - MMRM model with treatment, visit and treatment by visit as fixed effect; baseline as covariate; patient as random factor; unstructured covariance by visit. If the model does not converge a compound symmetry covariance structure will be used. Kenward-Roger method will be used to estimate the model degrees of freedom.
 -
- For weekly mean E-RS total score and SGRQ total score, additional analysis will be performed:
 - For weekly mean E-RS total score at 6, 12 and 24 weeks using ANCOVA approach, as described in Section **Error! Reference source not found.** of the SAP, all patients with baseline mean = 0 will be excluded.
 - For SGRQ total score at 6, 12 and 24 weeks, using ANCOVA approach, as described in Section 16.2.3.1 of the SAP, all patients with baseline assessment done after dosing time and date will be excluded.
 -

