9.0 STATISTICAL CONSIDERATIONS

9.1 Statistical Hypotheses

The aim of this study is to show superiority of ensifentrine over placebo regarding selected efficacy measures. The null hypothesis to be tested for each endpoint will be that there is no difference between ensifentrine and placebo, against the alternative hypothesis that ensifentrine is better than placebo. All tests will be two-sided at a 5% significance level. Primary and key secondary endpoints used for claims will be tested in a sequential order to preserve the alpha level. Testing will stop once a not significant result is achieved. Test order will be FEV₁ AUC_{0-12h} at 12 weeks, peak FEV₁ at 12 weeks, weekly mean E-RS total symptom score at week 24, SGRQ total score at 24 weeks, morning trough FEV₁ at Week 12, FEV₁ AUC_{0-4h} at 12 weeks and proportion of SGRQ responders at Week 24.

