7.4. MULTIPLE COMPARISONS/ MULTIPLICITY

To address multiplicity in the analysis of the endpoints, statistical testing of the primary endpoint and key secondary endpoints will be done in the hierarchical order (listed below). Initially the primary endpoint will be checked to see if comparison between active treatment and placebo is statistically significant. If yes, the first key secondary endpoint will be evaluated. If yes, the next key secondary endpoint will be evaluated. This process will continue until either all endpoints are evaluated, or if one of the endpoints' comparison is not significant.

Order of the endpoints that will be used for the hierarchical testing:

1. Change from baseline FEV₁ to FEV₁ AUC_{0-12h} at Week 12
2. Change from baseline FEV₁ to peak FEV₁ at Week 12
3. Change from baseline (i.e. mean over the last 7 days of run-in) to the mean weekly value at Week 24 in COPD symptoms, as measured by daily diary (E-RSTM:COPD)
4. Change from baseline in the SGRQ total score at Week 24
5. Change from baseline FEV₁ to morning trough FEV₁ at Week 12
6. Change from baseline FEV₁ to average FEV₁ AUC_{0-4h} at Week 12
7. Proportion of SGRQ responders at Week 24

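### SAP 16.2.4 places the key secondary sensitivity analyses at Week 12, but E-RS total, SGRQ total and SGRQ responders are tested at Week 24

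*SAP*

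**What the plan says.** The hierarchy in SAP Section 7.4 has the primary endpoint followed by six key secondary endpoints. Peak FEV1, morning trough FEV1 and FEV1 AUC0-4h are tested at Week 12. The other three are tested at Week 24: the weekly mean E-RS total, "Change from baseline in the SGRQ total score at Week 24" and "Proportion of SGRQ responders at Week 24". Protocol Section 9.1 gives the same weeks ("weekly mean E-RS total symptom score at week 24, SGRQ total score at 24 weeks", then SGRQ responders), and so does the estimand table in SAP Section 2.5.

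SAP Section 16.2.4 then introduces its list with "For the key secondary endpoints the following sensitivity analysis will be performed at Week 12". The list contains subgroup analyses, average imputation, a restricted multiple imputation (MI), range-method MI, a tipping-point analysis and a per-protocol (PP) analysis. It continues with an MMRM for the FEV1 endpoints and two exclusion analyses for E-RS and SGRQ.

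**The concern.** A sensitivity analysis is useful when it tests the result that carries the claim. For symptoms and quality of life that result is at Week 24. Protocol Sections 1.1 and 4.2 make the same distinction: 12 weeks is considered enough to show bronchodilation, and 24 weeks is there to inform on symptoms.

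If 16.2.4 is followed literally, the planned departures from missing at random (MAR) and the PP check for E-RS total and SGRQ total are run at a week that is not in the hierarchy. Withdrawals accumulate, so robustness at Week 12 does not establish robustness at Week 24. The documents treat withdrawal above 25% at 24 weeks as a possibility to plan for (Protocol Section 9.2, SAP Section 4.2), although as a trigger for adding patients and not as a forecast.

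**Working it through.** No figure in the plan bears on this point. The check is a comparison of sections and a count.

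**1. Does the opening sentence cover the Week 24 endpoints?** Yes. It speaks of the key secondary endpoints without restriction, and one item beneath it is "ANCOVA analysis with MI using the range data method as described in Section 16.2.2.3 for SGRQ total score and weekly mean total E-RS". The words limiting Week 12 to lung function occur in a single item, the restricted MI: "only considering baseline and Week 12 (for lung function parameters) in the imputation model".

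**2. What is planned for E-RS total and SGRQ total, and at which week?**

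| Analysis | Week | Departs from MAR? |
|---|---|---|
| Average imputation (16.2.4) | 12, by the opening sentence | Yes |
| Tipping point (16.2.4) | 12, by the opening sentence | Yes |
| PP with MI (16.2.4) | 12, by the opening sentence | No |
| Range-method MI (16.2.4) | 12 by the opening sentence; open when read with 16.2.3.1 | No (16.2.2.3 assumes MAR) |
| Exclusion of E-RS baseline of zero (16.2.4) | 6, 12 and 24 | No |
| Exclusion of SGRQ baselines taken after dosing (16.2.4) | 6, 12 and 24 | No |
| Extended mITT (16.4) | None stated | No |

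The MMRM item, "MMRM model with treatment, visit and treatment by visit as fixed effect", is written for the FEV1 endpoints only. Protocol Section 9.4.1 sets an MMRM for key secondaries including SGRQ total and E-RS total, but as the SAP stands it does not fill the gap. Where the authors wanted Week 24 they wrote it, as in "For SGRQ total score at 6, 12 and 24 weeks, using ANCOVA approach".

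**3. Does another section supply Week 24?** Protocol Sections 9.4.1 and 9.4.4 promise the PP and worst-case analyses without naming a week. SAP Section 16.2.2.4 assigns average imputation and tipping point to the key secondary endpoints, also without a week. SAP Section 16.1.2, which describes those methods, refers only generically to the visit concerned. SAP Section 3.3, the list of changes from the protocol, records no Week 12 limit.

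**4. Count.**

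- Key secondary endpoints: 3 at Week 12 + 3 at Week 24 = 6. The Week 24 endpoints hold positions 3, 4 and 7 of the 7 tests.
- Continuous Week 24 endpoints: 2 (E-RS total, SGRQ total).
- Departures from MAR: 2 methods × 2 endpoints = 4 results.
- PP: 1 × 2 = 2 results.
- Total under the Week 12 sentence: 4 + 2 = 6. Placed at Week 24 by any section in step 3: 0 of 6.

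Subgroup, range-MI and responder results are left out of the count. Protocol Section 9.4.1 promises subgroups only for some secondary endpoints. The week of range MI depends on how 16.2.3.1 is read. Section 16.2.2.4 does not say how the two methods carry over to a binary endpoint. For responders, SAP Section 3.3 also drops the protocol's non-responder sensitivity analysis.

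**The case against.** The strongest reply is that a key secondary endpoint is defined together with its week. On that view a sensitivity analysis of SGRQ total can only be at Week 24, Protocol 9.4.1 already promises PP evaluation of that variable, and the method text in 16.1.2 follows whichever visit the endpoint requires. The list does not obey its own opening sentence either, since two items run at Weeks 6, 12 and 24 and the MMRM is by visit. SAP Section 8 leaves table content to the output shells, so Week 24 tables may well exist. Finally, SAP Section 5.7 builds the PP set on discontinuation before Day 74 and on deviations that affect Week 12 lung function, so Week 12 may be deliberate for PP.

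Much of this supports reading the phrase as a drafting slip, and high confidence extends only to the mismatch in the text, not to the absence of Week 24 outputs. It does not remove the conflict. None of the cited sections names Week 24 for these analyses. Reading them with the endpoint definitions makes the opening sentence contradict the rest of the plan, and shells cannot correct SAP text. The PP argument has some force: without PP the count falls from 6 to 4, and those 4 are the departures from MAR. Week 12 subgroup results would not breach the protocol.

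**Conclusion.** The concern holds and should be fixed. As written, Section 16.2.4 puts six sensitivity results for E-RS total and SGRQ total at a week that is not tested, including all four planned departures from MAR for those endpoints. Taken literally, the plan would not show whether their Week 24 results are robust to the missing-data assumption. This rests on following the sentence as it stands, without correction from the shells. The main analyses, the hierarchy and alpha are not affected, and no size of effect on any estimate is claimed.

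**What to change.** In SAP Section 16.2.4, replace the Week 12 phrase with: *at the time point tested in Section 7.4 (Week 12 for the FEV1 endpoints; Week 24 for E-RS total, SGRQ total and SGRQ responders)*. If Week 12 only is intended, list it in Section 3.3 with the reason. The cost is one line and a few extra tables at Week 24, with no new data, analysis set or alpha. Settling the week before unblinding also avoids a later choice of time point.

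Three optional clarifications could be made at the same time; they are not part of the error:

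- When PP results are reported at Week 24, note that the single PP set is anchored to Day 74 and Week 12 lung function. This does not conflict with the treatment-policy estimand, which the main analysis addresses.
- State that the responder tipping point shifts the imputed SGRQ total, re-derives the 4-unit response and pools log odds ratios as in Section 16.2.2.2.
- Reconcile Section 16.2.2.2 (continuous method) with Section 16.2.3.2 (range method) for responder imputation.

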4.0 STUDY DESIGN

4.1 Overall Design

RPL554-CO-301 is a multicenter, randomized, double blind, parallel group, placebo controlled study to determine the efficacy and safety of ensifentrine 3 mg twice daily (BID) for 24 weeks with a subset of patients for 48 weeks, administered via nebulizer vs. placebo in patients 40 to 80 years of age with moderate to severe COPD (FEV₁ 30% – 70% of predicted, FEV₁/ forced vital capacity [FVC] ratio <0.7, with documented COPD symptoms).

Approximately 50% of patients recruited will be using stable background maintenance as *either* long-acting muscarinic antagonist (LAMA) *or* long-acting β 2 agonist (LABA) maintenance therapy and all patients will be provided with rescue albuterol/salbutamol for use as needed during the study. Up to 20% of patients are allowed to take inhaled corticosteroids during the study under certain provisions (see Sections 6.7.2 and 6.7.3). Washout of patients on stable background maintenance LAMA or LABA monotherapy for the sole purpose of study eligibility is not recommended.

Randomization will be stratified by three different factors: treatment duration (48 or 24 weeks), stable background maintenance LAMA or LABA therapy use (yes or no), and cigarette smoking (current or former). The 48 weeks strata will be randomized active to placebo 3:1, and the 24 weeks strata will be randomized active to placebo 1:1. Patients in the background maintenance LAMA or LABA therapy stratum must withhold Twice-Daily maintenance LAMA or LABA (or LAMA/ICS or LABA/ICS) for 24 hours and Once-Daily maintenance LAMA or LABA (or LAMA/ICS or LABA/ICS) for 48 hours prior to initiation of any spirometry. All patients must withhold short acting bronchodilator (SABA) rescue medication for at least 4 hours prior to initiation of any spirometry. All sites will use standardized spirometry and ECG equipment provided by a central vendor and all spirometry and ECGs will be over-read by the blinded central vendor.

Patients will be screened for eligibility before entering a 28-day run-in period to ensure a stable background maintenance LAMA or LABA bronchodilator medication regimen and to collect baseline information on symptoms and rescue medication use. Permitted rescue and background medications and the condition of their use during the study are described in Section 6.7.2. Prohibited medications and the prohibited time intervals prior to Screening are described in Section 6.7.3.

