9.4 Statistical Analyses

9.4.1 Efficacy Analyses

Efficacy analysis will primarily be performed on the mITT population. The primary endpoint and key secondary endpoints will also be evaluated using the PP population as a sensitivity analysis. Impact of imputations and various baseline characteristics will also be checked.

The primary endpoint, change from baseline in FEV₁ AUC_{0-12h} at Week 12, will be compared between treatments using an analysis of covariance (ANCOVA) model adjusting for treatment, region, background medication strata, and smoking status as factors and baseline FEV₁ as covariate. The estimated treatment difference with 95% confidence interval and associated (two-sided) p-value will be presented. Missing data will be imputed to get as close to the mITT population as possible. Primarily imputation will be based on data collected at visits performed after treatment withdrawal or at early termination visits even if outside the visit window. When no such data is available, imputation will primarily be done using multiple imputation based on baseline characteristics and secondarily, as a sensitivity analysis, by the average change in the opposite treatment group as randomized to as a worst-case scenario. Further details on the handling of missing data will be given in the Statistical Analysis Plan.

Key secondary endpoints, FEV₁ AUC_{0-4h}, peak FEV₁, morning trough FEV₁, SGRQ total score and weekly mean E-RS total score, and other continuous secondary or exploratory endpoints will be assessed repeatedly during the study and the change from baseline to pre-specified time point of evaluation will be compared by similar ANCOVA models adjusting for treatment, region, background medication strata and smoking status as factors and baseline as covariate. Data collected at visits performed after treatment withdrawal or at early termination visits will be used in the analyses. Remaining missing data will primarily be imputed using multiple imputation based on baseline characteristics and data collected at post-randomization visits. Since assessed repeatedly, in contrast to primary endpoint, these data will also be analyzed for sensitivity by mixed model repeated measures models with treatment, visit and treatment by visit interaction as factors, baseline as covariate, subject as random factor and covariance structure by visit.

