7. STATISTICAL CONSIDERATIONS

7.1. ADJUSTMENTS FOR COVARIATES AND FACTORS TO BE INCLUDED IN ANALYSES

The following covariates and factors are used in the analyses. For details of their inclusion in the models, see the specific analysis section.

Fixed effects: treatment (ensifentrine, placebo), region (Asia, Europe, North America), visit (Day 1, Week 6, Week 12, Week 18, Week 24), visit*treatment, stable background maintenance of LABA or LAMA (or LAMA/ICS or LABA/ICS) therapy use (yes, no), cigarette smoking (current, former)

Random effect: patient

Covariate: baseline

In case when the analysis model does not converge, the factor that causes it will be removed from the model.

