16.1.3. PRIMARY ANALYSIS OF PRIMARY EFFICACY VARIABLE

The primary objective of this study is to test the hypothesis that there is a difference between ensifentrine in comparison with placebo.

The change from baseline FEV₁ to average FEV₁ AUC_{0-12h} will be compared between ensifentrine and placebo using ANCOVA with fixed effects for treatment, region, background medication strata and smoking strata and baseline FEV₁ as covariate. Missing data will be imputed using imputation described in Section 16.1.2 of the SAP. The estimated treatment difference will be presented with 95% CI and associated p-value. Furthermore, SD will be presented for the treatment difference to check the sample size with 90% power. Summary statistics will be performed on the imputed values.

Model assumptions will be tested as per the following rules on the blinded data, before the DBL.

1. Residual vs Predicted plots will be created to check residuals are uncorrelated and normally distributed.
2. Normality of the data will be checked using Kolmogorov-Smirnov normality test.

If any of the checks specified above fail the test, then alternative approaches will be discussed, including different ways of transposing data. The SAP will be updated to reflect any changes prior to DBL.

Only spirometry measurements with best test review (BTR) grades “Acceptable” and “Borderline Acceptable” are used in the analysis and baseline calculations.

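### The MMRM sensitivity analysis of three FEV1 key secondary endpoints specifies a redundant random patient effect beside an unstructured covariance, leaves two competing non-convergence rules, and omits covariates used in the main analysis

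*SAP*

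**What the plan says.** SAP 16.2.4 describes the model as "MMRM model with treatment, visit and treatment by visit as fixed effect; baseline as covariate; patient as random factor; unstructured covariance by visit". The part at issue is "patient as random factor; unstructured covariance by visit". It then adds: "If the model does not converge a compound symmetry covariance structure will be used". No other fallback is named there. On inference it says that the "Kenward-Roger method will be used to estimate the model degrees of freedom".

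Protocol 9.4.1 has the same short model, ending with "baseline as covariate, subject as random factor and covariance structure by visit", and does not name the type of covariance.

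The main analysis of the same endpoints (SAP 16.2.3.1, referring to 16.1.3) is an "ANCOVA with fixed effects for treatment, region, background medication strata and smoking strata", with baseline as covariate. The multiple imputation model in SAP 16.2.2.1 uses the same region and strata variables.

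SAP 7.1 lists region, background therapy and smoking as available factors and patient as a random effect, but on covariates it says: "For details of their inclusion in the models, see the specific analysis section". It therefore does not put them into the MMRM. SAP 7.1 also has a general rule for models that fail to converge: take out whichever factor is responsible.

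SAP 16.2 gives the visits. Peak FEV1 and AUC0-4h are assessed on Day 1 and at Weeks 6, 12 and 24, and morning trough at Weeks 6, 12 and 24 only. SAP 16.2.4 sets the sensitivity analyses at Week 12.

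**The concern.** There are three linked problems.

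- **Redundancy.** A random intercept adds the same constant to every entry of the within-patient covariance matrix. An unstructured matrix can absorb that constant, so the data cannot tell the two apart. A programmer who follows the text literally codes a model with a flat direction in its likelihood.
- **Competing rules on failure.** Section 16.2.4 says to change the covariance to compound symmetry. Section 7.1 says to remove the offending factor, which here would arguably be the redundant patient effect, leaving the unstructured matrix in place. These are different analyses, and the plan does not say which rule governs. Nor does the 16.2.4 fallback say that the random effect is dropped, and a random intercept beside compound symmetry is redundant again.
- **Different covariates.** Because the MMRM lacks region, background medication and smoking, it differs from the ANCOVA both in how missing data are handled and in what is adjusted for. A discrepancy between the two could not be assigned to one cause.

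What is at stake is how well a supportive analysis can be interpreted and reproduced. No primary or hierarchical test depends on it.

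**Working it through.** **Reference figure.** The documents give no operating figure for the MMRM. The nearest is Protocol 9.2: SD 250 mL, 500 vs 300 evaluable, 59 mL, two-sided 5%, 90% power.

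- SE = 250 × sqrt(1/500 + 1/300) = 18.26 mL.
- Power = Φ(59/18.26 − 1.96) = 89.8%, so the stated 90% reproduces.

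The same SD and group sizes are used below only as a scale.

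**Step 1: identifiability.** Write V = σ_b²·J + R, with J the all-ones matrix and R unstructured. R has p(p+1)/2 parameters.

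| Endpoints | Visits p | R | Plus σ_b² | Rank |
|---|---|---|---|---|
| Peak FEV1, AUC0-4h | 4 | 10 | 11 | 10 |
| Morning trough FEV1 | 3 | 6 | 7 | 6 |

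On simulated four-visit data (assumed SD 250 mL, correlations 0.50 to 0.65, n = 800), setting R = S − σ_b²·J, with S the sample covariance matrix, gave the same log-likelihood, −18554.690951, for σ_b² = 0, 5000, 15000 and 25000. Only the split between σ_b² and R is undetermined. V itself, and hence the treatment contrasts, is identified.

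**Step 2: the fallback as written.** Compound symmetry is V = σ₁·J + σ²·I. Keeping the random intercept adds σ_b²·J, which gives three parameters at rank 2. Without the random effect, the fallback goes from 10 parameters (6 for morning trough) to 2, with nothing in between.

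**Step 3: effect of compound symmetry on the Week 12 SE.** With complete data, compound symmetry replaces the Week 12 variance by the average over visits, so model SE / true SE = sqrt(mean of SD²) / SD at Week 12. Actual alpha = 2 × (1 − Φ(1.96 × ratio)). The documents give no SDs by visit, so the patterns are assumptions.

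| Assumed SDs, Day 1 / Wk 6 / Wk 12 / Wk 24 (mL) | Pooled SD (mL) | Ratio | Alpha |
|---|---|---|---|
| 250 / 250 / 250 / 250 | 250.0 | 1.000 | 0.0500 |
| 200 / 240 / 250 / 270 | 241.4 | 0.965 | 0.0585 |
| 180 / 230 / 250 / 290 | 240.8 | 0.963 | 0.0591 |
| 270 / 260 / 250 / 240 | 255.2 | 1.021 | 0.0454 |

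The range 0.045 to 0.059 illustrates the effect and is not a bound. The pattern 180 / 230 / 250 / 270 gives sqrt(220700/4) = 234.9 mL, ratio 0.940 and alpha 0.066.

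Morning trough has no Day 1 value. For that last pattern its pooled SD is sqrt((230² + 250² + 270²)/3) = 250.5 mL and the ratio 1.002, so the error practically disappears. For 230 / 250 / 290 it is 257.9 mL, ratio 1.032 and alpha 0.043. The same rising trend that makes the four-visit endpoints anti-conservative leaves morning trough about right or conservative.

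**Step 4: effect of the omitted covariates.** If region, background medication and smoking jointly explain a partial R² of the residual variance (not given; 0 to 0.10 assumed), omitting them multiplies the SE by 1/sqrt(1 − R²).

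| Partial R² | SE factor | SE (mL) | Power for 59 mL |
|---|---|---|---|
| 0 | 1.000 | 18.26 | 89.8% |
| 0.02 | 1.010 | 18.44 | 89.2% |
| 0.05 | 1.026 | 18.73 | 88.3% |
| 0.10 | 1.054 | 19.25 | 86.6% |

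**The case against.** The strongest reply is that the text may only be loose. Naming patient as a random factor may be shorthand for patient as the subject in the repeated-measures statement, and then only wording is at fault. This is possible. But SAP 7.1 separately lists patient as a random effect and Protocol 9.4.1 says much the same, so a literal reading is natural and the wording should exclude it.

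Several stronger readings are tempting but not supported.

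- A reader might infer that the check will probably run under compound symmetry. The documents do not show this. Software may set the redundant variance to zero and converge, a singular Hessian is not in itself non-convergence, and the SAP 7.1 rule could restore exactly the unstructured model wanted.
- A reader might infer that the treatment effects are biased or inestimable. They are not; only the variance split is undetermined.
- A reader might infer that compound symmetry makes standard errors systematically too small. The sign depends on SDs that the documents do not give. Errors at Week 24 are beside the point, because these analyses are at Week 12.
- A reader might infer that the MMRM alone drops all the stratification factors. Treatment duration is a stratification factor (Protocol 4.1) but is missing from the ANCOVA too, and region is not a stratification factor.
- A reader might infer that the SAP departs from the protocol. The short covariate list comes from Protocol 9.4.1.

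Two further points stand. Protocol 9.4.1 motivates the MMRM by the repeated assessments rather than as a test that isolates missing data, and SAP 16.2.4 has other missing-data checks: average imputation, tipping point, and imputation from baseline and Week 12 only. Omitting prognostic covariates from a randomized linear model mainly costs precision. These points limit the consequence but do not make the specification coherent.

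**Conclusion.** The random patient effect is wrong as written: beside an unstructured covariance it is redundant for all three endpoints. The practical consequence is an avoidable risk of numerical failure, followed by a choice between two rules that the plan leaves open. How likely that failure is cannot be established from the documents.

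If compound symmetry were reached, the Week 12 error could go either way. The alpha figures rest on assumed visit SDs, complete data and a normal approximation. Kenward-Roger corrects for estimating the covariance, not for choosing the wrong structure.

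The missing covariates are a free improvement rather than an error. The SE cost of 0 to 5% rests on an assumed partial R² of 0 to 0.10.

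Severity is low. This is a supportive analysis, and the primary analysis, the testing hierarchy and the sample size do not change.

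**What to change.** In SAP 16.2.4, before unblinding:

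1. Delete the random patient effect and model within-patient correlation only through the unstructured by-visit covariance, with patient as the repeated-measures subject.
2. Add region, background medication strata and smoking strata as fixed effects, to match the ANCOVA and the imputation model.
3. State that the convergence rule in 16.2.4, not the general one in 7.1, governs this model.
4. Put a structure that allows unequal variances by visit, such as heterogeneous compound symmetry or heterogeneous Toeplitz, ahead of plain compound symmetry. The exact choice is a matter of preference; what matters is that the order is fixed in advance.

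The cost is a few lines of SAP text and model code. No new data are needed.
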